8.3 Secondary objectives

- To determine the functionality of the immune response to full and fractional doses at the 1-month post-boost time point using an opsonophagocytic assay.
- To compare vaccine efficacy against carriage of non-PCV10 serotypes 6A and 19A in the full dose PCV13 arms when compared to the fractional dose arms, using the full dose PCV10 2p+1 arm as a control, with primary analyses at 18 months of age and secondary analyses at 9 months of age. The carriage prevalence of the common vaccine serotypes (PCV10 serotypes) in the fractional dose arms will also be compared against the carriage prevalence in the full dose arms.
- To compare frequency and severity of local injection-site reactions and vaccine-related adverse events in the 28 days following immunization after fractional dose delivery and a full dose delivery.
- To determine the concentration of circulating IgG after the primary series of the 2p+1 schedule, prior to boost, at 9 months of age and after the boost at 18 months of age, estimate the duration of direct protection conferred by full and fractional dose schedules and use seroepidemiology to monitor acquisition rates.
- To compare carriage prevalence at 9 and 18 months of age and IgG concentrations at 4 weeks after the primary series after full dose of PCV10 in a 3p+0 schedule, and full/ fractional doses of PCV10/13 in a 2p+1 schedule.

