9 TRIAL DESIGN

9.1 Overall Study Design

A phase IV individually-randomised controlled trial of full or fractional (20% or 40%) doses of PCV10/ PCV13, given as a 3-dose schedule to infants: 2 doses at 6 and 14 weeks of age and a booster dose at 9-12 months (the 2p+1 schedule) or 3 full doses at 6, 10 and 14 weeks of age (the 3p+0 schedule) (Figure 1.).

At 6-8 weeks of age, 300 infants will be enrolled at random into each of the seven trial arms and followed until 18 months of age. The seven trial arms:

- A. Full dose PCV13 vaccination in a 2p+1 schedule.** This arm will demonstrate immunogenicity and carriage endpoints for an alternative schedule to 3p+0 as recommended by WHO, in the Kenyan population.
- B. 40% fractional dose PCV13 vaccination in a 2p+1 schedule.**

C. 20% fractional dose PCV13 vaccination in a 2p+1 schedule.

[figure not shown]
D. Full dose PCV10 vaccination in a 2p+1 schedule. This arm will demonstrate immunogenicity and carriage endpoints for an alternative schedule to 3p+0 as recommended by WHO, in the Kenyan population.

E. 40% fractional dose PCV10 vaccination in a 2p+1 schedule.

F. 20% fractional dose PCV10 vaccination in a 2p+1 schedule.

G. Full dose PCV10 vaccination in a 3p+0 schedule. This arm would represent the current vaccine and schedule in the Kenyan routine immunisation programme and would act as an additional comparison arm.

Figure 1. Clinical trial flow

¹ Immunogenicity samples at 9 and 18 months of age will only be drawn from 150/300 participants in each arm.
RI = routine immunisation.

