11 LAB PROCEDURES

11.1 Blood sample management & testing

Venous blood samples will be collected at baseline (2ml), the D84 visit (approximately 18 weeks of age; 2ml) and, in trial arms A-F, at the 1-month post-boost visit (10-13 months of age; 2ml). Half of the participants enrolled onto trial arms A-F (150 in each arm) will have additional blood draws at 9 months and 18 months of age (2ml at each visit). A cumulative total of 4-10mls of blood will be collected from each participant by the end of the trial, depending on randomisation and allocation. The sample at baseline will be tested for anaemia in order to inform clinical care of the infant. All serum will be separated within 48 hours of sample collection and stored at -20 degrees Celsius at the KWTRP CGMR-Coast laboratories. All samples will be shipped to the UCL WHO Reference Laboratory for Pneumococcal Serology based at the Great Ormond Street Institute of Child Health. If any remaining volume is not shipped to UCL, samples will be stored at the KWTRP CGMR-Coast laboratories. Sample management will include monitoring of the number of freeze-thaw cycles experienced by each sample in a laboratory database.

At the UCL WHO Reference Laboratory for Pneumococcal Serology, sera will be assayed for antibodies to all vaccine-type capsular polysaccharides using the WHO reference ELISA following adsorption with cell wall polysaccharide and 22F polysaccharide at a concentration of 10 mcg/ ml (Details available at <http://www.vaccine.uab.edu/ELISA%20Protocol.pdf>). This assay is based on the original Wyeth assay used to generate the correlate of protection of 0.35 mcg/ml.

A subset of 50 sera from each of the trial arms A-F, at the 1 month post-boost time point will be used to estimate the functionality of the immune response to all vaccine serotypes using the multiplexed Opsono-Phagocytic Assay (MOPA; details available at <http://www.vaccine.uab.edu/UAB-MOPA.pdf>).

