The required sample size for the trial was calculated in order to ensure good power to detect both the primary and secondary immunogenicity endpoints, this approach is recommended in trials where both primary and secondary endpoints are important to determine the success of the intervention[77]. The proportion of children achieving the correlate of protection (IgG ≥ 0.35 $\mu\text{g/ml}$) varies across PCV10/13 serotypes after the primary vaccination series and by schedule (range 63.5-98.4%)[33, 76, 78-80]. In a prior study of PCV7 in Kilifi, the average proportion of children reaching the threshold antibody concentration across serotypes at 18 weeks of age was 87%[33]. The average proportion reaching the threshold antibody concentration at 18 weeks of age after 2 primary doses, 2 months apart, in European[81], Israeli[17, 82] and South African children[24] was also approximately 87% across 10 serotypes but serotype specific responses ranged between 63-97%. On this basis, to detect non-inferior immunogenicity (% responders) to 10 of the 13 serotypes in the PCV13 arms or 8 of the 10 serotypes in the PCV10 arms at 18 weeks of age with 90% power, we would need to enrol 300 infants per arm to declare non-inferiority using a margin of 10%, accounting for serotype-specific response rates, multiple serotype-specific comparisons and 5% loss to follow up at 4 weeks after the booster dose. Additionally, this sample size would allow us to perform an analysis on *all* vaccine types with a 12% non-inferiority margin with 84% power.

The 10-12% non-inferiority margin has been determined considering the public health consequences of a commensurate loss of protection, assuming 87% of infants achieve protection with the full dose.

There will be >99% power to declare non-inferiority using the criterion that the lower limit of the 95% CI for the ratio of GMCs (fractional/full dose) is >0.5. Based on the IgG GMCs elicited post boost in South Africa, which ranged between 13 and 35 mcg/ml for the PCV7 serotypes[24], we hope to be able to estimate GMCs with precision +/- 2-4 mcg/ml.

There will therefore be four pairwise comparisons of each vaccine type serotype for the primary endpoint of non-inferiority (i.e. full dose vs 20% dose; and full dose vs. 40% dose for each vaccine).

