The results from the multiplex opsono-phagocytic assay (MOPA) to all vaccine serotypes plus 6C will be used to compare IgG functionality after 3 full doses of PCV10 or PCV13 with that after 3 fractional doses of PCV10 or PCV13 at 1-month post boost. Antibody function will also be compared between products for comparable schedules. The correlation between IgG concentration and functional activity following a third dose of PCV delivered in a 2+1 schedule will be assessed. Exploratory analyses will derive a functional correlate of protection against carriage using the post booster MOPA titre and vaccine type carriage at 18 months of age for serotypes 19A and 6A.

To evaluate the safety of the fractional dose delivery we will describe:

- the proportion of infants in each trial arm experiencing specified local vaccination site reactions (e.g. redness, swelling) within the 30 minutes immediately after vaccination as observed by study personnel;
- the proportion experiencing local/systemic adverse reactions, e.g. injection site abscess, in the 7 days after vaccination, as reported by mother or the legal guardian who accompanied the infant to the vaccination session at a day 8 visit.

We do not expect to have the statistical power to determine a difference in the risks of injection site abscess between arms as the risk of injection site abscess is expected to be low. Pentavalent vaccine delivered in 10-dose vials in Kenya resulted in 128 abscesses per 100,000 injections[84]. If this baseline level of risk applies to the 3 immunisations given to 1200

children in the fractional dose groups we would expect to see no more than 5 abscesses throughout the whole study.

The sera of all participants in the seventh trial arm (Arm G) will be assayed for immunogenicity to 7 serotypes (the PCV7 vaccine types) at 4-weeks post-primary series only. The proportion of responders in Arm G at 4-weeks post-primary series will be compared to that of the PCV10/13 2p+1 arms at 4-weeks post-primary series. Non-inferiority will be achieved if the lower limit of the 95% confidence interval (CI) around the difference in the proportion of 'responders' (2p+1 - 3p+0) is $>-10\%$ [76]. Assuming the proportion of children reaching the threshold antibody concentration across serotypes at 18 weeks of age is on average 87%[33], with 300 per arm, we would have 85% power to declare non-inferiority using a margin of 10%, accounting for 7 serotype-specific comparisons.

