IgG GMCs in a random selection of half the participants in trial arms A-F at 9 months of age (pre-boost) and at 18 months of age (9 months post-boost) will be used to 1) estimate the duration at which GMCs remain above the threshold for protection in the first 2 years of life after a 2p+1 schedule of full or fractional doses and 2) to monitor carriage acquisition rates.

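### The functional (MOPA) dose comparison rests on 50 sera per arm; IgG already planned on about 235 other post-boost sera per arm could sharpen it without another assay

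*Combined protocol and SAP*

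**What the plan says.** The first secondary objective in section 8.3 is "To determine the functionality of the immune response to full and fractional doses at the 1-month post-boost time point using an opsonophagocytic assay". Section 11.1 assigns "A subset of 50 sera from each of the trial arms A-F, at the 1 month post-boost time point" to the MOPA. It does not say how the 50 are picked. By contrast, section 13.2 describes the persistence half-sample as "IgG GMCs in a random selection of half the participants in trial arms A-F at 9 months of age".

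For IgG, section 11.1 says that "sera will be assayed for antibodies to all vaccine-type capsular polysaccharides using the WHO reference ELISA", with no subset at the post-boost visit in arms A-F. That visit is the primary time point, and section 10.7 says that the safety board's review must wait for the results of all participants.

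On analysis, section 13.2 says that the MOPA results, for all vaccine serotypes and 6C, "will be used to compare IgG functionality after 3 full doses of PCV10 or PCV13 with that after 3 fractional doses". It adds: "The correlation between IgG concentration and functional activity following a third dose of PCV delivered in a 2+1 schedule will be assessed". No estimator, margin, power or precision is given for MOPA. Section 13.3 leaves the detail to a statistical analysis plan to be finalised before database lock.

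**The concern.** This is a two-phase sample: a correlated measure (IgG) on everyone in the arm and an expensive measure (MOPA) on a subset. A comparison of 50 titres with 50 titres carries the chance difference in IgG between the 50 chosen and the rest of their arm. That difference will be known from the trial's own data and can be removed. The plan expects IgG and function to be related, since it will estimate their correlation, but it does not say that it will use this to improve the dose comparison.

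What is at stake is the precision of each serotype's answer to whether function is preserved at the lower doses. The silence on selection matters separately: inference from the 50 to the arm needs a random, or known-probability, sample whichever estimator is used.

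**Working it through.** **Figures in the plan.** There is no MOPA figure to reproduce. The neighbouring ones hold up. The 6A/19A carriage power with 300 per arm comes out at 91.6% for 19% v 9.5% (stated 92%) and 78.5% for 19% v 11% (stated 78%). For IgG, a precision of ±2 around 13 implies an ln SD of ln(15/13) × √285 / 1.96 = 1.23, and ±4 around 35 implies 0.93. Both give power above 99.9% for the 2-fold criterion (stated >99%).

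**Inputs.**
- Arm size: "300 infants will be enrolled at random into each of the seven trial arms" (section 9.1).
- Loss: "5% loss to follow up at 4 weeks after the booster dose" (section 13.1).
- Post-boost sera per arm: N = 300 × 0.95 = 285.
- MOPA sera per arm: n = 50, leaving 285 − 50 = 235 with IgG only.
- Correlation ρ between log IgG and log MOPA within an arm: not in the documents; assumed 0 to 0.8.

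**Formula.** The variance of the regression estimate of an arm's mean log MOPA titre, relative to the plain mean of 50, is

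f = (1 − ρ²)[1 + (1 − n/N)/(n − 3)] + ρ² n/N.

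Here n/N = 0.1754 and (1 − 0.1754)/47 = 0.0175, so f = 1.0175(1 − ρ²) + 0.1754ρ². For ρ = 0.7: 1.0175 × 0.51 + 0.1754 × 0.49 = 0.519 + 0.086 = 0.605. With the same n, N and ρ in both arms, f also applies to the log titre ratio.

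| Assumed ρ | f | SE ratio √f | Change in SE | Effective sera 50/f |
|---|---|---|---|---|
| 0 | 1.018 | 1.009 | +0.9% | 49 |
| 0.3 | 0.942 | 0.970 | −3% | 53 |
| 0.5 | 0.807 | 0.898 | −10% | 62 |
| 0.7 | 0.605 | 0.778 | −22% | 83 |
| 0.8 | 0.479 | 0.692 | −31% | 104 |

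**Simulation.** Ten thousand two-arm trials per setting gave variance ratios of 0.938, 0.812 and 0.615 at ρ = 0.3, 0.5 and 0.7, in line with the formula.

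**Robustness.** A second simulation (8,000 two-arm trials per setting, slope fitted within arm) tried harder cases. With correlations of 0.8 in one arm and 0.5 in the other, with a curved relation fitted by a straight line, and with both plus a detection floor, bias stayed below 0.001 log10, coverage was 95%, and the SE ratio was 0.78 to 0.80. At zero correlation the SE ratio was 1.006.

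**Interval width.** The 95% interval for the titre ratio is multiplied and divided by exp(1.96 × SD × √(2f/50)), with f = 1 for the plain comparison. The SD of log titre is also an assumption. For an ln SD of 1.0, 1.5 and 2.0, the factor is 1.48, 1.80 and 2.19 with 50 sera alone, and 1.36, 1.58 and 1.84 with IgG at ρ = 0.7.

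**The case against.** The strongest reply is that nothing is wrong as written. Arms are randomised, and 50 against 50 is valid if the subset is representative. MOPA is a secondary comparison with no non-inferiority claim. Section 13.2 gives one sentence of purpose, names no estimator and does not rule IgG out, and the detailed analysis plan is still to come. All of this stands. A reader might infer that the plan confines the comparison to the 50 titres, or that the 50 will be hand-picked. The text says neither; it is silent on both.

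Three limits also stand.
- The estimand is open. Section 13.2 speaks of IgG functionality, which could mean function per unit of IgG. For that quantity the IgG-only sera add little, so the gains above apply only to the arm-level titre ratio.
- 6C is in the MOPA panel, but the planned ELISA covers vaccine types only, so 6C has no IgG to borrow from.
- The gain depends on a correlation that the documents do not give. At 0.3 it is slight.

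These points limit the proposal but do not remove it. The estimator uses data that the trial will hold anyway, and its cost when the correlation is absent is negligible.

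**Conclusion.** A worthwhile, inexpensive improvement to a secondary objective. The gain in SE runs from about 3% at a correlation of 0.3 to about 31% at 0.8, somewhat less where many titres sit at the detection floor, and the loss is under 1% at zero. It assumes random selection of the 50, 285 post-boost sera per arm, slopes fitted within arm, and the arm-level titre ratio as the target.

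Two stronger readings are not supported. One is that MOPA is underpowered against a 0.5 bound: the plan sets that bound for IgG concentrations only and none for MOPA, so there is no MOPA power to fall short of. The other is that the 9- and 18-month IgG samples need the same treatment. Their stated uses are the duration above the threshold and carriage acquisition rates, which gain little from narrower arm means, so any extension there is optional.

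**What to change.** - **Section 11.1:** state that the 50 MOPA sera are a simple random sample of each arm's post-boost sera.
- **Section 13.2, estimand:** state that the functional comparison is the fractional/full ratio of arm-level MOPA geometric mean titres, by serotype.
- **Section 13.2, estimator:** for each vaccine serotype with a matching ELISA result, regress log MOPA on log post-boost IgG within each arm, with a separate slope per arm, and average the predictions over all the arm's post-boost sera. Report the ratio with a 95% interval that allows for the two-phase sampling, and the raw 50-versus-50 ratio beside it.
- **Exceptions:** leave 6C as the raw comparison, and report any function-per-unit-IgG comparison separately.
- **Margin:** add no non-inferiority bound for MOPA.

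The cost is a few sentences in the plan and a little more analysis work, plus reliance on a simple working model. No further sera, assays or infants are needed. Writing it into the analysis plan before database lock avoids choosing the estimator after seeing the titres.

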11.2 Nasopharyngeal swab sample management & testing

Standard methods for administering and processing nasopharyngeal swabs for culture will be used to ensure that results are comparable with previous studies[74, 75]. A single, deep, nasopharyngeal rayon swab will be taken at 9 and 18 months of age and transported in 1 ml skim milk-tryptone-glucose-glycerin (STGG) transport medium to the KWTRP CGMR-Coast laboratories. A primary culture will be prepared on blood agar with gentamicin before the sample is frozen at -70C. One colony on the plate will be selected at random for serotyping by latex agglutination and confirmatory Quellung reaction. Polymerase Chain Reaction (PCR) will be performed for quality control purposes on 10% of the samples and as a confirmatory test for samples that have ambiguous or negative Quellung tests. Minor serotypes, relative abundance and density may be assessed at a later date using the stored samples should the initial culture results prove difficult to interpret. Carriage will be defined if a serotype is isolated by latex agglutination and confirmatory Quellung reaction[75]. Swab medium will be stored at the KWTRP CGMR-Coast laboratories.

12 ASSESSMENT OF SAFETY

12.1 Identification of Adverse Events (AEs) and Severe Adverse Events (SAEs)

Measures will be put in place to identify any adverse or serious adverse events (including any cases of pneumococcal disease) in study participants:

- Study staff will assess the general health of the child at every study visit;
- Fieldworkers based in the communities around each study clinic will be educated in the signs and symptoms of respiratory distress in infants and will visit every child at home for their 7-day post vaccination check-up. They will also be points of contact in the community to help parents access study staff for medical advice and referral if necessary.
- Parents will be told verbally and it is written in the informed consent form that they should contact study staff for free medical consultation and treatment in case of any illness in their child. Parents will be given the phone number of the clinical officers on the trial and their local fieldworker.
- Hospital staff at the Kilifi and Malindi referral hospitals will be sensitised about the trial and asked to notify study staff if they suspect a child presenting to the hospital (for any reason) is a study participant.

Any AE will be evaluated for seriousness (see section 12.2), relatedness, severity and expectedness by the treating physician. Solicited and unsolicited AE and SAE will be recorded in all participants in the CRF. If further medical attention is needed, the study team will organise referral and emergency admission to Kilifi County Hospital.

12.2 Definitions and monitoring of AEs and SAEs

AEs and SAEs will be defined in accordance with the International Conference on Harmonization (ICH) Guidelines for Good Clinical Practice (38).

An adverse event (AE) is defined as:

Any untoward medical occurrence in a clinical trial subject to whom a vaccine has been administered; it does not necessarily have a causal relationship with the vaccine/vaccination. Definitions of AEs and grading, when applicable, to be followed in the study sites will be specified in an SOP.

A serious adverse event (SAE) is any untoward medical occurrence that:

- Results in death
- Is life threatening: if the participant was at risk of death at the time of the event; it does not refer to an event that hypothetically might have caused death if it were more severe
- Results in persistent or significant disability/incapacity: if the event results in a substantial disruption of the participant's ability to carry out normal life functions. This definition is not intended to include experiences of relatively minor medical significance such as headache, nausea, vomiting, diarrhoea, influenza, injection site reactions and accidental trauma (e.g. sprained ankle)
- Requires in-patient hospitalization or prolongation of existing hospitalization: in general, hospitalization signifies that the participant has been detained (usually involving at least 24h stay) at the hospital or emergency ward for treatment that would not have been appropriate in an outpatient setting
- Is a congenital anomaly/birth defect in the offspring of a study participant
- Is an important medical event that may jeopardize the participant or may require intervention to prevent one of the other outcomes listed above.

Hospitalization for either elective surgery related to a pre-existing condition, which did not increase in severity, or frequency following initiation of the study, or for routine clinical procedures (including hospitalization for "social" reasons) are not considered as SAEs. When in doubt as to whether "hospitalization" occurred or was necessary, the AE will be considered serious.

The definition of a routine clinical procedure is a procedure, which may take place during the study period and should not interfere with the study vaccine administration or any of the ongoing protocol specific procedures. If anything untoward occurs during an elective procedure and satisfies any of the criteria for SAE, this will be documented and reported.

12.3 Reporting AEs and SAEs

Both PCV10 and PCV13 are licensed products and had been administered to over 109 million children in LMICs by the end of 2016[34].

All AEs that are not serious will not be reported individually but will be recorded in the CRF and summarised in an annual safety report.

All SAEs will be reported individually using an SAE form including an assessment of relatedness, severity and expectedness. The treating physician will ensure that as much information as possible is provided in the SAE form and if necessary will discuss with the PI or designee prior to submission. The PI will receive the SAE form within 24 hours of the event. If the event is life threatening, and/or suspected to be related to the vaccination the PI (or designee) will be informed by telephone within 24 hours of the event. Specimens from study participants presenting with respiratory disease will be cultured in order to detect whether the respiratory disease is pneumococcal and whether any pneumococcal disease is vaccine-type.

The minimum information required for the initial SAE report:

- Participant's study number, age and sex
- Description of the event
- Date of vaccination (s)
- Reporter information
- Preliminary assessment of relatedness
- Severity
- Preliminary assessment of expectedness

The principal investigator (PI) (or designee) will ensure that the information provided on the SAE form, is legible, does not have abbreviations or personal and institutional identifiers, and is as complete as possible. The PI (or designee) is responsible for safety monitoring and reporting SAEs and updates of SAEs to the DSMB, Sponsor, IRB/IEC and regulatory authorities as appropriate (Table 6). Those that are life-threatening or suspected to be causally related to vaccination will be reported to the DSMB, Sponsor and vaccine manufacturers, this will include any cases of suspected vaccine-type pneumococcal disease at any time point in the study follow-up.

All SAEs identified will be tabulated and reported annually in summary form to Kenyan Regulatory Authorities and the LSHTM ethics committee.

